5.5 Treatment Compliance

PCLX-001 will be dispensed to patients to be taken orally on an ambulatory basis as well as during clinic visits.

During ambulatory treatment, patients will document the intake of PCLX-001 in a compliance diary.

Unused PCLX-001 study drug will be returned by patients. The time and amount of study drug intake will be recorded in the compliance diary. Each patient's compliance will be evaluated by the study center. This information will be transferred into the eCRF taking into account each dose interruption and / or any changes in dosing.

To ensure the required number of patients are evaluable Cycle 1 DLT dose-escalation cohorts, participants will need to have received at least 21-days of the planned total dose (unless a DLT occurs). Patients non-compliant in Cycle 1 will be replaced.

Any discrepancies between actual and expected amount of returned study medication must be discussed with the patient at the time of the visit, and any explanation must be documented in the source records.

6. NON-STUDY THERAPIES

6.1 Concomitant Therapy

Concomitant therapy includes any prescription medications or over-the-counter preparations used by a participant between the 7 days preceding the baseline evaluations and the end of last study visit. All concomitant medications (including start / stop dates, total daily dose, and indication), including vaccinations, should be reported by the Investigator and recorded on the appropriate eCRF.

Permitted Therapies

- Patients may receive palliative and supportive care for any underlying illness.
- Patients may receive vaccinations for COVID-19. Ideally, vaccinations would not be administered during Cycle 1 of study treatment, however, this is not prohibited.
- Corticosteroids use for cytoreduction due to malignancy-related symptom control of B-cell lymphoma may be given prior to initiation of study treatment (up to 100 mg/day of prednisone or equivalent for no more than 5 days).
- Palliative radiotherapy during the study will be allowed for local pain control if:

- In the opinion of the investigator, the patient does not have progressive disease.
- Not more than 10% of the patient's bone marrow is irradiated.
- The radiation field does not encompass a target lesion; the indication for radiation therapy to a target lesion is considered progressive disease.
- The safety of oral PCLX-001 administered concomitantly to radiation therapy has not been determined. Therefore, oral PCLX-001 treatment should be held on those days where the patient receives palliative radiotherapy, and restarted the day after completion of palliative radiotherapy.
- Patients may continue receiving bisphosphonates prophylactically or for bone metastases while on study treatment.
- Granulocyte colony-stimulating factor and other hematopoietic growth factors may be used for the management of acute toxicity, such as febrile neutropenia, when clinically indicated or at the investigator's discretion, except their preventive use in Cycle 1.
- CYP3A4 substrates should be used with caution, as exposure may be higher or lower when concomitantly administered with PCLX-001 due to CYP3A4 inhibition or induction, respectively.
- P-gp substrates (e.g. aliskiren, ambrisentan, colchicine, dabigatran etexilate, digoxin, fexofenadine, maraviroc, posaconazole, ranolazine, saxagliptin, sitagliptin, talinolol, tolvaptan) should be used with caution.

Prohibited Therapies

- Use of PPIs must be discontinued at least 48 hours prior to initiation of study drug.
Note: If a potential participant is on a PPI and requires some form of acid reducing agent, the investigator should consider alternatives for the duration of the trial, including Famotidine, or oral antacid drugs such as calcium carbonate.
- Patients may not receive another investigational treatment or other approved antitumor therapy (such as chemotherapy) while on this protocol. In addition, treatment with "non-conventional therapies" (such as herbal supplements) is not permitted.
- The use of strong CYP3A4 inhibitors and inducers is not permitted from 5 days prior to first administration of study drug to the active FU visit.
- Patients should not receive PAXLOVID as components are known to inhibit CYP3A.
- Patients may not receive granulocyte colony-stimulating factor and other hematopoietic growth factors for primary prevention during Cycle 1.

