4.2 Exclusion Criteria

The following exclusion criteria apply to ALL (Dose-escalation and expansion) patients:

1. Known hypersensitivity to the study drugs or excipients of the preparations or any agent given in association with this study
2. History of cardiac disease: congestive heart failure New York Heart Association (NYHA) class > II, unstable angina (angina symptoms at rest), new-onset angina (within the past 6 months before study entry), myocardial infarction within the past 6 months before study enrollment date, or uncontrolled cardiac arrhythmias
3. Uncontrolled arterial hypertension despite optimal medical management (per investigator's opinion)
4. Moderate or severe hepatic impairment, i.e. Child-Pugh class B or C
5. Patients with known human immunodeficiency virus (HIV) infection
6. Patients who have an active hepatitis B virus (HBV) or hepatitis C virus (HCV) infection requiring treatment. Patients with chronic HBV or HCV infection are eligible at the investigator's discretion provided that the disease is stable and sufficiently controlled under treatment.
7. Patients with significantly impaired liver function as assessed by the following laboratory tests to be conducted within 7 (± 3) days before the first dose of study drug:
 - Total bilirubin \geq 1.5 times the upper limit of normal (ULN), and/or
 - Alanine aminotransferase (ALT) and aspartate aminotransferase (AST) \geq 3 times ULN or \geq 5 times ULN for patients with malignant liver involvement.
8. Infections of CTCAE Grade 2 not responding to therapy or active clinically serious infections of CTCAE Grade > 2
9. Symptomatic metastatic brain or meningeal tumors unless the patient is $>$ 3 months from definitive therapy, has a stable imaging study within 4 weeks prior to the first dose of study drug and is clinically stable with respect to the tumor at the time of study entry. Patients with asymptomatic brain metastases must not be on steroid therapy. Patients with neurological symptoms should undergo a CT / MRI scan of the brain to exclude new or progressive brain metastases.
10. Current or past history of central nervous system (CNS) lymphoma

11. Uncontrolled seizure disorder requiring therapy (e.g. strong CYP3A4 inducers such as carbamazepine and phenytoin)

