12. History of organ allograft transplantation or autologous stem cell transplantation \leq 3 months prior to the first dose of study drug. Patients who received prior CAR-T or other T-cell targeting treatment (approved or investigational) \leq 4 weeks prior to study drug administration
13. Evidence or history of bleeding disorder, i.e. any hemorrhage / bleeding event of CTCAE Grade $>$ 2 within 4 weeks before the first dose of study drug
14. Serious, non-healing wound, ulcer, or bone fracture
15. Previous or concurrent cancer that is distinct in primary site or histology from the cancer being evaluated in this study, with the exception of the following previous or concurrent cancer types:
 - Curative treatment for localized cancer completed without signs of recurrence and treatment-related toxicity and low risk of recurrence as assessed by the investigator,
 - *In-situ* prostate cancer, Gleason Score $<$ 7, prostate-specific antigen $<$ 10 ng/mL (very low risk and low risk, according to therapy guidelines, e.g. the National Comprehensive Cancer Network guideline; active surveillance / observation is a recommended option).
16. Any clinical condition that is considered unstable or might jeopardize the safety of the patient and his / her compliance in the study
17. Inability to swallow oral medications
18. Any malabsorption condition
19. Breastfeeding. Female patients must not breastfeed during treatment and until 4 months after last study drug administration.
20. Treatment with anticancer chemotherapy or immunotherapy during the study or within 3 weeks before the first dose of study drug. For small-molecule drugs, a period of at least 3 half-lives before the first dose of study drug is acceptable. Mitomycin C or nitrosoureas should not be given within 6 weeks before the first dose of study drug.
21. Treatment with systemic steroids (prednisone dose \geq 10 mg/day or equivalent dose).
22. Acute toxic effects (CTCAE Grade \geq 2) of previous anticancer chemotherapy or immunotherapy that have not yet stabilized or if significant post-treatment toxicities have been observed. (Note however that toxic effects of previous anticancer therapy considered as chronic, such as chemotherapy-induced neuropathy, fatigue, alopecia, or anorexia of CTCAE Grade $<$ 2, for which further resolution is not expected, do not prevent participation in this study.)

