7. STUDY SCHEDULE AND ASSESSMENTS

7.1 Study Calendar

The calendar below lists the assessments and indicates with an "X" the visits when they are performed. Baseline evaluations are to be conducted within 28 days (or 7 days as indicated) prior to start of protocol therapy. Diagnostic imaging and LVEF assessment must be done 28 days prior to the start of therapy. In the event that the patient's condition is deteriorating, laboratory evaluations should be repeated within 72 hours prior to initiation of the next cycle of therapy.

Table 7A: Schedule of Evaluations (Study Flow Chart) – SCREENING

Measures / actions	Screening	
	Within 28 days	Within 7 (± 3) days before the first dose of PCLX-001
Informed consent		
Signing of informed consent	X	
Archival tumor tissue ^a	X	
General screening procedures	X	
Check of inclusion / exclusion criteria	X	
Demographics	X	
Complete medical history including documentation of primary diagnosis ^b	X	
Abbreviated medical history		X
Baseline characteristics		
• Prior and concomitant medications (prescribed and OTC)	X	
• Baseline toxicities	X	
Assessment of toxicities (open questioning for AEs)		X
Concomitant medications (prescribed and OTC)		X
Physical examination ^j	X	
Vital signs		
• Blood pressure, heart rate, and body temperature	X	
Body weight and body height	X	
ECOG performance status assessment	X	
Cardiovascular safety assessment		
• 12-lead ECG (standard, triplicate)	X	
• MUGA scan or echocardiogram	X	

Table 7A: Schedule of Evaluations (Study Flow Chart) – SCREENING (continued)

Measures / actions	Screening	
	Within 28 days	Within 7 (± 3) days before the first dose of PCLX-001
Tumor assessment (CT or MRI) ⁱ	X	
Blood sample collection for tumor biomarker, if applicable (e.g. CA125, CEA)	X	
PET-CT (optional, NHL patients only) ^c	X	
Fresh tumor biopsy (optional) ^d		X
Blood sample collection for exploratory biomarker analyses		X
Blood / urine sample collection for laboratory safety assessments		
• Hematology ^e ,		X
• Blood chemistry ^f ,		X
• Calculation of eGFR by Cockcroft-Gault		X
• Coagulation (aPTT, PT/INR)		X
• Thyroid function (TSH and T ₄ [total or free per local standard])		X
• Virology (HBsAg, anti-HCV) ^g		X
• Pregnancy test (serum) ^h		X
• Urinalysis (dipstick)		X

- a. Archival tumor tissue is mandatory for patients enrolled in the dose escalation levels and expansion cohorts. This specimen could have been collected at any time from the initial diagnosis to study entry.

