- b. If a patient discontinues study treatment at any time during the study for any reason (except for patients who died, withdrew consent and objected to further data collection, or were lost to FU), an active FU assessment should be performed 30 days (± 4 days) after the last dose of the last study drug.
- c. Prescribed and OTC.
- d. Questioning for AEs will be conducted at clinic visits; in addition, spontaneous reports of AEs will be collected throughout the study.
- e. PK sampling: For patients in dose escalation, see Table 7C for schedule. For patients in dose expansion, see Table 7D for schedule.
- f. To be taken pre-dose of each cycle Day 1 within 60 min before the morning dose and EOT
- g. Hematology includes CBC + differential (i.e. hemoglobin erythrocytes, leukocytes, platelets, MCV, RDW, hematocrit, neutrophils, lymphocytes, monocytes, eosinophils, basophils, immature granulocytes, nucleated RBCs). Detection of CTCAE Grade 4 neutropenia (only Cycle 1) will trigger twice-weekly white blood cell counts to be performed, so that DLT determination can be made.
- h. Blood chemistry includes: sodium, potassium, chloride, bicarbonate or total CO² (as per site practice), calcium, phosphate, magnesium, total protein, albumin, glucose, serum creatinine, urea, uric acid, total bilirubin, ALT, AST, LDH, alkaline phosphatase, lipase.
- i. Window for tumour assessment is ± 5 days from Day 28 of the even-numbered cycles. CT of the relevant disease region for solid tumors and CT thorax, abdomen, pelvis \pm neck for NHL.
- j. Women of childbearing potential (including women of childbearing potential whose partners are sterilized) must have a negative pregnancy test.
- k. This scan should only be performed for NHL patients and is optional (i.e. not required for patients with other histologies). If a PET-CT is performed at screening, it should be repeated once after the sixth cycle if no progressive disease is detected during the course of treatment and / or to confirm complete response or disease progression.
- l. Exam to be symptom-directed.
- m. To be performed if clinically indicated (e.g. positive HBsAg and/or anti-HCV tests as performed during screening).
- n. Unless otherwise indicated, the window for visits is ± 2 days.
- o. Electronic records will be used to assess patient survival monthly (± 1 week) from the date of the follow-up visit.

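### Section 6.1 permits pre-treatment steroid in lymphoma without reconciling it with exclusion 21, and the baseline scan may precede the steroid, so a partial response could include steroid shrinkage

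*Combined protocol and SAP*

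**What the plan says.** Section 6.1 lists among the permitted therapies: "Corticosteroids use for cytoreduction due to malignancy-related symptom control of B-cell lymphoma may be given prior to initiation of study treatment". The limit is "up to 100 mg/day of prednisone or equivalent for no more than 5 days". It gives no interval between the last steroid dose and Day 1.

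Exclusion 21 in Section 4.2 (repeated in the synopsis) reads "Treatment with systemic steroids (prednisone dose", with a threshold of 10 mg/day or more, or the equivalent. It has no look-back period and no lymphoma exception. The lead-in to the list is "The following exclusion criteria apply to ALL (Dose-escalation and expansion) patients".

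On baseline imaging, Section 7.1 says both "Baseline evaluations are to be conducted within 28 days (or 7 days as indicated) prior to start of protocol therapy" and "Diagnostic imaging and LVEF assessment must be done 28 days prior to the start of therapy". Table 7A puts tumour CT or MRI in the within-28-days column. Nothing there, in Section 7.3 or in the efficacy population of Section 8.2 links the scan or the analysis to steroid use.

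**The concern.** There are two separate problems.

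The first is eligibility. A lymphoma patient who takes the course that Section 6.1 allows has also received a dose above the exclusion 21 threshold. Whether that patient may enrol depends on how a site reads two rules that do not mention each other.

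The second is attribution. The permitted steroid is meant to shrink tumour. If the baseline scan comes first, shrinkage between that scan and Day 1 is measured as if it occurred on PCLX-001. The trial has no control arm to reveal this. Preliminary single-agent activity is the secondary objective, and Section 3.5 names the response rate among the inputs to the recommended Phase II dose.

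The protocol closes similar routes elsewhere. Exclusion 20 sets a gap after earlier anticancer treatment, exclusion 23 sets 21 days after radiotherapy to target lesions, and Section 6.1 treats a need to irradiate a target lesion on study as progression. The cytoreductive steroid has no matching safeguard.

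**Working it through.** **Eligibility: the two rules side by side**

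| | Section 6.1 | Exclusion 21 |
|---|---|---|
| Who | B-cell lymphoma | all patients, both parts |
| Dose (prednisone or equivalent) | permitted up to 100 mg/day | excluded at 10 mg/day or more |
| Duration | at most 5 days | not stated |
| Timing | before study treatment, no washout | not stated |
| Cross-reference | none | none |

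The rules agree if exclusion 21 means steroid use still ongoing at entry, or if Section 6.1 is an exception to it. Neither section says so.

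**Sequence of scan, steroid and response assessment**

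- The baseline scan can be up to 28 days before Day 1. If the sentence fixing imaging at 28 days prior is taken literally, any steroid given in the last four weeks follows the scan.
- The steroid course lasts at most 5 days, at any time before Day 1.
- Response scans are timed "from Day 28 of the even-numbered cycles", within 5 days either way. The first is at 28 + 28 = Day 56, so Day 51 to Day 61.

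**Which responses depend on the baseline scan (Appendix C)**

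- CT-based partial response needs a fall of at least 50% in SPD (the sum of the products of perpendicular diameters). It is relative to baseline. Partial metabolic response is also judged against baseline uptake.
- CT-based complete response (target nodes at or below 1.5 cm, no extralymphatic disease) and complete metabolic response (score 1 to 3) are largely absolute standards. The timing of the baseline scan matters little for them.

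**Effect on the partial-response threshold**

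Let *s* be the share of SPD lost to the steroid after the scan and still absent at the response scan. The further fall needed for partial response is 1 − 0.50/(1 − *s*). The documents give no value for *s*, so the range is assumed.

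| Assumed *s* | Further fall needed |
|---|---|
| 0% | 50.0% |
| 10% | 44.4% |
| 20% | 37.5% |
| 30% | 28.6% |
| 40% | 16.7% |
| 50% | 0% |

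**Effect on the Cohort B response rate**

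The plan states no target response rate, hypothesis or power for Cohort B, so there is no figure to reproduce. Section 8.1 gives 20 patients per cohort.

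- One misattributed response adds 1/20 = 5 points. Moving from 2/20 to 3/20 takes the estimate from 10% (exact 95% CI 1.2% to 31.7%) to 15% (3.2% to 37.9%).
- The expected inflation is (1 − *p*) × *f* × *q*. Here *p* is the true response rate, *f* the share given steroid after the scan, and *q* the chance that an exposed non-responder is then counted as a partial response. All three are assumed.
- With *p* = 10%, and *f* and *q* each from 10% to 30%, the result runs from 0.9 × 0.1 × 0.1 = 0.9 points to 0.9 × 0.3 × 0.3 = 8.1 points. With *f* = 50% and *q* = 30% it is 13.5 points. If *f* or *q* is zero, it is zero.

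The spread comes wholly from the assumed inputs. It shows sensitivity and does not estimate the bias.

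**The case against.** A reader might infer that the protocol contradicts itself outright and that every patient given the permitted steroid is ineligible. The documents do not support that. Section 6.1 is a narrow permission (lymphoma, symptom control, pre-treatment, five days), and treating a specific rule as an exception to a general one is natural. This objection stands as far as it goes. It does not remove the need for the protocol to say which reading applies.

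A reader might also infer that the Cohort B response rate will be biased upward, by 5 to 10 points or so. That is not supported either. The steroid effect would have to persist for about eight weeks after Day 1 in relapsed or refractory disease. Growth between an early baseline scan and Day 1, or regrowth after the steroid stops, would push the other way. Complete responses are largely untouched. The frequency of use is not stated. These points stand, and they reduce the bias to a possibility of unknown size.

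The stakes are also limited. Cohort B has no response threshold or test, its intervals are wide, and the response rate is one of several inputs to the dose decision. Section 6.1 already requires dose, start and stop dates and indication for concomitant medications, so exposed patients can be identified. What is missing is any planned use of that information.

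**Conclusion.** The eligibility conflict is real on the text: the two steroid rules are not reconciled, and sites could decide differently on the same patient. That holds whatever the size of any bias.

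The attribution problem is a gap in the design. Nothing prevents the baseline scan from preceding a cytoreductive steroid, so steroid shrinkage could contribute to a partial response in lymphoma patients, in Cohort B and in Part A. Solid-tumour patients are not affected. Each misattributed response would be worth 5 points in Cohort B. How many there would be depends on use, timing and persistence of effect, none of which the documents give, and the number may be zero.

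The point deserves correction because the remedy is cheap and protects a single-arm response rate. It does not invalidate the design.

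**What to change.** 1. Reconcile exclusion 21 with Section 6.1, in the body and the synopsis, so that one reading applies at all sites. This review takes no position on which steroid rule is right. In the same edit, reconcile the Section 7.1 sentence on imaging 28 days prior with the within-28-days column of Table 7A, because the next item depends on it.
2. Where a cytoreductive steroid course is planned, schedule the baseline scan used for response after the last steroid dose, inside the existing screening window. Where the scan has already been done when the need arises, do not require a repeat, but flag the patient.
3. Using the steroid dose and dates already recorded in the eCRF, pre-specify a listing of exposed lymphoma patients and report Cohort B response with and without them.

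The cost is protocol wording, slightly tighter screening logistics for symptomatic patients, and one additional sensitivity line. No extra scan or new data collection is needed.

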1.2.3 PCLX-001 Pharmacokinetics and Pharmacology

Mouse Pharmacokinetics

PCLX-001 was dosed as a bolus solution intravenously at 3 mg free base/kg (5% DMSO; 95% sterile water) or by gavage orally as a solution at 10 mg free base/kg (5% DMSO; 40% PEG400; 55% sterile water) to female NMRI mice (n=3/dose route). Blood samples (10 µL) were taken from each mouse at 5 (IV only), 15, 30 minutes, 1, 2, 4, 6 and 8 hours post-dose, mixed with two volumes of distilled water and stored frozen until analysis.

Following intravenous administration at 3 mg free base/kg, PCLX-001 mean blood clearance was low at 3mL/min/kg (~3% liver blood flow), mean volume of distribution (V_{ss}) was low at 0.4 L/kg, resulting in a moderate mean half-life at 1.6 hours. Mean AUC_{0-8} was 1,119,500 ng·min/mL.

Following oral administration at 10 mg free base/kg, PCLX-001 had a mean C_{max} of 11,200ng/mL and median t_{max} at 2 hours. Mean AUC_{0-8} was 3,400,810 ng·min/mL and mean bioavailability recorded at 91%.

PCLX-001 was not brain penetrant in mouse models (B:B ratio following a 1 mg/kg IV dose is 0.04 at 5- and 30-minutes post-dose).

Rat Pharmacokinetics

PCLX-001 was dosed as a bolus solution intravenously at 1 mg free base/kg (5% DMSO; 95% saline) or by gavage orally as a solution at 3 mg free base/kg (5% DMSO; 95% sterile water) to male Sprague Dawley rat (n=2 IV; n=3 PO). Blood samples (10 µL) were taken from each rat at 5 (IV only), 15, 30 minutes, 1, 2, 4, 6 and 8 hours post-dose, mixed with two volumes of distilled water and stored frozen until analysis.

Following intravenous administration at 1 mg free base/kg, PCLX-001 mean blood clearance was low at 15 mL/min/kg (~18% liver blood flow), mean volume of distribution (V_{ss}) was moderate at 1.3 L/kg, resulting in a moderate mean half-life at 1 hour. Mean AUC_{0-8} was 67,230 ng·min/mL. Blood clearance was well aligned to hepatic extraction (E_H) at 16%, determined from a separate male Sprague Dawley rat hepatic portal vein study following oral dosing at 3 mg free base/kg.

Following oral administration at 3 mg free base/kg, PCLX-001 had a mean C_{max} of 170ng/mL and median t_{max} at 4 hours. Mean AUC_{0-8} was 52,868 ng·min/mL and mean bioavailability 26%.

Dog Pharmacokinetics

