PCLX-001 is a substrate for P-glycoprotein, as demonstrated by efflux studies in CaCo2 cells. It is not a substrate for or OAT1, OAT3, OCT1, OCT2, OATP1B1, OATP1B3, MATE1, MATE2K or BRCP. Overall, PCLX-001 shows a low probability for drug-drug interaction.

PCLX-001 was not mutagenic in the Ames test.

In vitro hERG Testing

A non-GLP study was done by a group developing a proprietary system for human ether-á-go-go-related (hERG) analysis (<https://www.achlys-inc.com/Cardiomyocytes>). The negative controls were acetylsalicylic acid and chloramphenicol and the positive control (determined IC₅₀ of 0.9 μ M) was Thioridazine Hydrochloride. PCLX-001 had a determined IC₅₀ of 9.9 μ M. This concentration was well above that expected to be achieved in a human phase I trial and suggests that PCLX-001 is likely not to be cardiotoxic.

KINOMEscan

PCLX-001 is a small molecule inhibitor that theoretically could also have the ability to inhibit kinases, and cause unexpected off-target effects. PCLX-001 was screened *in vitro* at concentrations of 0.5, 10, and 100 μ M (269, 5380, and 53,800 ng/mL) for its ability to inhibit the activity 468 human kinases. PCLX-001 at concentrations up to 10 μ M (5380 ng/mL) did not inhibit any kinase. PCLX-001 at 100 μ M (53,800 ng/mL), a concentration ~4000 x greater than the EC50 of PCLX-001 for BL2 cells, produced meaningful inhibition of only three kinases: MRCKA, PIP5K2B, and SRPK1. Based on these results, PCLX-001 is unlikely to produce adverse effects in patients due to off-target kinase inhibition and appears to be NMT-specific.

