1.2.4 PCLX-001 Toxicology and Safety Profile

Non-GLP Toxicity and Safety Profile:

Tissue of control and PCLX-001 treated (with doses up to 50 mg/kg subcutaneous daily injection) NOD/SCID mice were studied after formalin fixation and paraffin-embedding, followed by immunohistochemical staining. There was no morphologic evidence of toxicity of PCLX-001 on small intestine, kidney, liver, or bone marrow. Blood counts and standard biochemical testing of blood from treated and untreated mice revealed no evidence of marrow, renal, or hepatic toxicity.

PCLX-001 is >90% orally bioavailable in mice and dogs and 26% in rats, has a half-life from oral dosing of 10 mg/kg of 5.7 hours in mice and 3.9 hours in dogs, and is well-tolerated by mice, rats, and dogs with a maximum tolerated dose in 14-day repeat dose toxicity studies of >75 mg/kg in rats and 4 mg/kg in dogs. Based on a body surface area scaling of the 50 mg/kg dose that resulted in complete tumor remission in most mouse xenografts of hematologic malignancies (BL, DLBCL, AML), the effective human dose is projected to be ~4 mg/kg daily (250 mg for a 70 kg individual).

GLP Non-Clinical Safety Testing:

PCLX-001 was evaluated for safety in 4-week oral toxicity studies with 2-week recovery periods in rats at 50, 125, and 300 mg/kg/day and dogs at 2, 4, 8, and 12 mg/kg/day, performed to GLP standards (Weickert *et al*, 2020). The highest non-severely toxic dose levels (HNSTDs) were 125 mg/kg/day for male rats, 300 mg/kg/day for female rats, and 4 mg/kg/day for dogs of both sexes. At higher dose levels, dose-limiting toxicity occurred within the first few days, was similar in both species, and was attributed to GI mucosal damage and decreased hematopoiesis, with secondary complications such as dehydration and inflammation.

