23. Radiotherapy to target lesions in the 21 days before starting the first dose of study drug. Palliative radiotherapy is allowed to non-target lesions at any time before starting the first dose of study drug.
24. Major surgery or significant trauma within 4 weeks before the first dose of study drug
25. Previous assignment to treatment during this study
26. Concomitant participation in another clinical study with investigational medicinal product(s)
27. Substance abuse, medical, psychological, or social conditions that may interfere with the patient's participation in the study or evaluation of the study results
28. Close affiliation with the investigational site; e.g. a close relative of the investigator, dependent person (e.g. employee or student of the investigational site)
29. Use of strong CYP3A4 inhibitors and inducers from 14 days prior to first administration of study drug. Strong CYP3A4 inhibitors and inducers are prohibited during the study and until the active FU visit.
30. Use of Proton Pump Inhibitors (PPIs) must be discontinued at least 48 hours prior to initiation of study drug.

Note: If a potential participant is on a PPI and requires some form of Acid Reducing Agent(s) (ARAs), the investigator should consider alternatives for the duration of the trial, including Famotidine, or oral antacid drugs such as calcium carbonate.

31. Clinically relevant findings in the ECG such as a second- or third-degree atrioventricular block, prolongation of the QRS complex > 120 ms (except for bundle branch block pattern), or prolongation of the QTc interval (Fridericia) over 450 ms unless agreed otherwise between the investigator and the sponsor's medically responsible person.

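### PCLX-001 is reported as a P-gp substrate, but Section 6.1 cautions only on other P-gp substrates and is silent on P-gp inhibitors and inducers (minor safety precaution)

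*Combined protocol and SAP*

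**What the plan says.** Section 1.2.3, under the in vitro ADME profile, reports the transporter result: "PCLX-001 is a substrate for P-glycoprotein, as demonstrated by efflux studies in CaCo2 cells". The same short paragraph ends with the sponsor's overall view: "Overall, PCLX-001 shows a low probability for drug-drug interaction".

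Section 6.1, under permitted therapies, contains the plan's only P-gp instruction: "P-gp substrates (e.g. aliskiren, ambrisentan, colchicine, dabigatran etexilate, digoxin, fexofenadine, maraviroc, posaconazole, ranolazine, saxagliptin, sitagliptin, talinolol, tolvaptan) should be used with caution". The bullet before it deals with CYP3A4 and, unlike the P-gp bullet, gives a reason: "CYP3A4 substrates should be used with caution, as exposure may be higher or lower when concomitantly administered with PCLX-001".

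Inhibitors and inducers are restricted on CYP3A grounds only. The prohibited list in Section 6.1 says "The use of strong CYP3A4 inhibitors and inducers is not permitted", and exclusion criterion 29 in Section 4.2 says "Strong CYP3A4 inhibitors and inducers are prohibited during the study and until the active FU visit". The prohibited list also bars PAXLOVID because it inhibits CYP3A, as well as herbal supplements and other antitumour treatment. Outside Sections 1.2.3 and 6.1, P-gp appears only in the list of abbreviations.

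**The concern.** A drug carried by a transporter is exposed to whatever changes that transporter's activity. If P-gp carries PCLX-001, a P-gp inhibitor could raise its exposure and an inducer could lower it. A caution on other P-gp substrates chiefly protects those other drugs, and would matter most if PCLX-001 itself inhibited or induced P-gp. The documents report no such finding. The rule therefore guards the direction without reported data and leaves out the direction with data.

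Safety, the maximum tolerated or recommended Phase II dose, and PK are the primary objectives (Section 2). Escalation decisions rest on Cycle 1 DLTs in cohorts of 3 to 6 patients (Section 3.1). An unplanned change in exposure during Cycle 1 would be a safety matter for that patient and would make that patient's PK profile harder to interpret.

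**Working it through.** This is mainly a check of text. Setting the two interaction routes side by side:

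| Question | CYP3A4 | P-gp |
|---|---|---|
| Reported in vitro (Section 1.2.3) | PCLX-001 inhibits it, IC50 12.1 µM | PCLX-001 is a substrate |
| Rule on drugs carried or metabolised by it (Section 6.1) | Caution, with reason | Caution, no reason |
| Rule on inhibitors and inducers of it (Sections 4.2 and 6.1) | Strong agents banned | None |

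The empty cell is the bottom right one. It is also the cell to which the reported P-gp result points.

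**Do other bans fill the cell?** The CYP3A4 ban covers strong agents only and is defined by CYP3A4 activity. PAXLOVID is barred for CYP3A inhibition. The herbal and antitumour bans are defined by type of therapy. Some P-gp inhibitors or inducers may be caught by one of these, but the documents name none and do not say how far the overlap goes.

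**Would an interaction be seen afterwards?** Largely yes, if someone looks.
- Concomitant medications are recorded with dates, dose and indication (Section 6.1) and checked on Cycle 1 Days 1, 8, 15 and 22 (Table 7B).
- Part A PK is sampled on Cycle 1 Days 1, 2, 8, 15 and 22, with post-dose profiles on Days 1 and 15 (Table 7C).
- Individual concentrations are listed by patient (Section 8.5).
- Data for all patients at a level are reviewed before the next level opens (Section 3.1). However, the items that Section 11.2 requires for that review are treatment administration, adverse effects, laboratory results, optional bone marrow results and normal ranges. Neither concomitant medications nor PK is listed, although further information may be requested.

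These steps detect an interaction; they do not prevent one.

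**Can the effect be sized?** The only relevant figures are the animal bioavailabilities: "PCLX-001 is >90% orally bioavailable in mice and dogs and 26% in rats". They reproduce from Section 1.2.3 as F = (oral AUC / oral dose) / (IV AUC / IV dose):
- Mouse: (3,400,810 / 10) / (1,119,500 / 3) = 340,081 / 373,167 = 0.91, against 91% stated.
- Rat: (52,868 / 3) / (67,230 / 1) = 17,623 / 67,230 = 0.26, against 26% stated.
- Dog: (560,220 / 10) / (42,140 / 1) = 56,022 / 42,140 = 1.33, against 133% stated. This match takes both AUCs in ng·min/mL, although the oral one is printed per hour.

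None of these gives a usable bound on a P-gp effect:
- The dog figure compares 10 mg/kg oral with 1 mg/kg IV, while Section 1.2.4 reports more-than-proportional exposure in dogs. A value above 100% may therefore reflect non-linear kinetics.
- The mouse AUCs stop at 8 hours, against an oral half-life of 5.7 hours (Section 1.2.4).
- The rat AUCs also stop at 8 hours, with oral tmax at 4 hours, and come from "male Sprague Dawley rat (n=2 IV; n=3 PO") only. No document attributes the rat's low bioavailability to P-gp.
- Oral bioavailability in any species says nothing about inducers or about P-gp's part in elimination.

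The size is therefore not stated.

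**The case against.** The strongest case against is that no consequence is demonstrated. The sponsor reported the P-gp result and, in the same paragraph, concluded that interactions are unlikely, and nothing in the documents contradicts that. No permitted P-gp inhibitor or inducer is named. Several bans already narrow the field, and Section 12.6 refers to an Investigator Brochure, not among these documents, which may say more. Dosing is staggered (Section 3.4), and drug-related Grade 3 or higher events put accrual on hold (Section 10.5).

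Most of this stands, and it keeps the point minor. It does not fill the gap. The overall statement comes with no P-gp inhibitor or inducer data in these documents. The sponsor also thought P-gp worth a caution in Section 6.1, so the caution should cover the drugs that the reported result concerns.

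Two stronger readings are tempting. A reader might turn the bioavailabilities into a fold-change, either negligible (mouse, dog) or large (rat). The data support neither, for the reasons in the working. A reader might also infer, from cohorts of 3 to 6, that one affected patient would distort a dose level's PK summary or its DLT count by a known share. One patient's share of a small cohort follows from cohort size alone. It measures no distortion, and nothing in the documents shows a biased DLT count.

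**Conclusion.** The gap is real and minor. The conclusion rests on the absence of any mention of P-gp inhibitors or inducers in these documents, and on the general principle that a transporter's inhibitors and inducers can alter exposure to its substrates. It assumes that the in vitro P-gp result has some relevance in patients, which the documents neither confirm nor exclude. Neither the change in PCLX-001 exposure nor the number of patients affected can be given. The point does not call the dose-escalation rules or the MTD determination into question.

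**What to change.** Add a bullet to Section 6.1 along these lines: *PCLX-001 is a P-gp substrate; P-gp inhibitors and inducers should be used with caution, and avoided where an alternative exists, at least through Cycle 1 and PK sampling days.* The sponsor should supply examples, as it does for substrates, so that sites can act on it.

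Flag any such use in the PK listings, and have the flag available at the safety cohort review. It can be drawn from the concomitant-medication data already recorded. The flag is for interpretation only and should not be used to re-decide whether an event counts as a DLT.

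The cost is one bullet, one derived flag and a small limit on co-medication choice, since this is a caution and not a ban. No new visit, sample or data field is needed.
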